Inclusion Criteria:

- \geq 40 years of age as of the year of the index date
- At least one pharmacy claim for Stiolto Respimat or Trelegy Ellipta between 15 September 2017 and 31st March 2020.
 - For Stiolto Respimat users, the first pharmacy claim of FDC of Tiotropium + Olodaterol (5/5 mcg) will be defined as the index date.
 - For Trelegy Ellipta users, the first pharmacy claim of FDC of Fluticasone Furoate + Umeclidinium + Vilanterol (100/62.5/25 mcg), will be defined as the index date.
- Two medical claims (at least one claim on index date or before in the baseline period) with an ICD-9/10 diagnosis code(s) for COPD in any position during the study period (baseline ± post index date).
- At least one year of continuous medical and pharmacy health plan eligibility prior to the index date is required (to allow a baseline period for the covariates and characterizing the study population).

Exclusion Criteria:

- To increase the likelihood of a true diagnosis of COPD, we will exclude all patients with two medical claims of asthma, cystic fibrosis, lung cancer, or interstitial lung disease in any position on separate dates of service during the study period.
- To restrict the cohort to first line maintenance therapy of Stiolto Respimat or first line maintenance therapy of Trelegy Ellipta we will exclude; patients on LAMA. monotherapy; LABA monotherapy; ICS monotherapy; free or FDC of ICS+LABA, LAMA+LABA, ICS+LABA+LAMA therapy within six months prior to index date.
- Pharmacy claims for multiple index medications on the index date.
- Pharmacy claims for non-index COPD maintenance medications on the index date.

Proprietary confidential information © 2022 Boehringer Ingelheim International GmbH or one or more of its affiliated companies

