9.3 VARIABLES

The definitions for exacerbations are as below.

- A severe exacerbation will be defined as follows:
 - An inpatient admission or an ER visit with a COPD diagnosis code in the primary position; or
 - An inpatient admission or an ER visit with a diagnosis code for acute respiratory failure in the primary position and a COPD diagnosis code in any position; or
 - An inpatient admission or an ER visit with a diagnosis code for acute respiratory failure in the primary position + an inpatient admission or an ER visit within ±7 days with a COPD diagnosis code in any position.
- A moderate exacerbation will be defined as follows:
 - An ambulatory (office or outpatient) visits with a COPD diagnosis code in any position + a pharmacy claim for an oral corticosteroid (OCS) prescription within ±7 days of the office/outpatient visit; or

Proprietary confidential information © 2022 Boehringer Ingelheim International GmbH or one or more of its affiliated companies

- \circ An office or outpatient visit with a COPD diagnosis code in any position + a pharmacy claim for respiratory antibiotic prescription within ±7 days of the office/outpatient visit; or
- An office or outpatient visit with a COPD diagnosis code in any position + a pharmacy claim for an OCS + a pharmacy claim for respiratory antibiotic prescription within ±7 days of the office/outpatient visit.
- Pneumonia diagnosis: Binary indicators will be created to identify patients with a diagnosis of 1) pneumonia (Appendix 1). The time to first pneumonia diagnosis, and time to first pneumonia, during follow-up will also be captured.
- Pneumonia-related hospitalization: Binary indicators will be created to identify
 patients with an acute hospitalization with diagnosis of 1) pneumonia in any
 position (Appendix 1) The time to first pneumonia-related hospitalization during
 follow-up will also be captured.
- COPD exacerbation and/or pneumonia diagnosis: Binary indicators will be created to identify patients with each of the following composite outcomes: severe COPD exacerbation or an acute hospitalization with a diagnosis of pneumonia in any position, severe COPD exacerbation or a hospitalization with a diagnosis of pneumonia in any position, any COPD exacerbation or pneumonia diagnosis in any position, and any COPD exacerbation or pneumonia diagnosis in any position. Time to event variables will be created for each composite outcome during the follow-up period.

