9.3.2 Outcomes

9.3.2.1 Primary Outcomes

The primary outcome event for effectiveness is time to first COPD exacerbation after cohort entry. The event is defined as follows:

- Severe exacerbation:
 - Hospitalization with a principal discharge diagnosis of COPD and/or
 - An emergency department (ED) visit with a discharge diagnosis of COPD
 - An inpatient admission or an ER visit with a diagnosis code for acute respiratory failure in the primary position and a COPD diagnosis code in any position
- Moderate exacerbation:
 - \circ An antibiotic for a respiratory condition dispensed \pm an OCS

Time to the first COPD exacerbation will be measured from index date until the occurrence of a hospitalization for COPD (severe exacerbation) or ED visit for COPD (severe exacerbation) or prescription of an antibiotic \pm an OCS on the same day (moderate exacerbation). Severe and moderate exacerbations were considered as a composite for main analyses. Sensitivity analyses will include stratification by exacerbation severity.

Exacerbations will be categorized as moderate or severe and a count of any (severe or moderate), severe, and moderate will be provided.

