9.3.3 Covariates

Patient characteristics at baseline will be assessed for Stiolto and Trelegy users overall and stratified by history of exacerbation.

The covariates included in the Propensity Score Matching (PSM) will include all the below covariates including the ones defined during the 12-month pre-index baseline period and chronic comorbid conditions.

- Gender
- Age group (years, categorical and a continuous variable)
- Calendar year of cohort entry
- Region
- Insurance type (e.g., Commercial, Medicare)
- Season of index date (winter, spring, summer, fall)

Additional characteristics that will be defined during the 12-month pre-index baseline period:

- Previous acute COPD exacerbation (measured both overall and in the 30 days prior to cohort entry), categorized as 0, 1, or ≥2.
 - All exacerbations (Moderate+Severe)
 - Hospitalizations (Severe)
- Use of other respiratory drugs in the 12-month pre-index period:
 - Short-acting beta-agonists
 - Short-acting Anticholinergics
 - Methylxanthines
 - o LAMA
 - o LABA

Proprietary confidential information © 2022 Boehringer Ingelheim International GmbH or one or more of its affiliated companies

- o ICS
- o ICS/LABA
- Use of antibiotics commonly prescribed for a respiratory condition (e.g., azithromycin)
- Use of OCS
- Oxygen Use
- Pulmonary Rehabilitation

Chronic comorbidities were defined using diagnoses identified during all available data prior to the index date, and included

- Quan-Charlson Comorbidity Index score/individual comorbidities
- Cardiovascular disease
- Diabetes
- Renal failure
- GERD
- Arthritis
- Osteoporosis
- Cancer (excluding basal cell carcinoma)
- Baseline pneumonia diagnosis
- Baseline acute bronchitis diagnosis
- Diagnosis of dyspnea during baseline identified using ICD 9 786.0x and ICD 10 R06.0x
- Diagnosis of obesity during baseline identified using ICD 9 278.xx and ICD 10 E66.xx
- Diagnosis of alcohol dependence during baseline identified using ICD 9 303.xx, 305.0x and ICD 10 F10.xx
- Smoking dependence during baseline identified using ICD 9 305.1 and ICD 10 F17.xx
- Tobacco use or cessation counselling*

*We anticipate limited capture of lifestyle variables known to be risk factors and potential confounders, including obesity, smoking status, and excessive alcohol consumption.

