9.7.1 Main analysis

Analyses will be presented comparing Stiolto vs Trelegy overall after PSM matching and stratified as follows if the sample size allows (at least 15% in each strata):

• Low history of exacerbation: 0 inpatient (i.e., severe exacerbations) and 0-1 outpatient events (i.e., moderate exacerbations)

Proprietary confidential information © 2022 Boehringer Ingelheim International GmbH or one or more of its affiliated companies

• High history of exacerbation: ≥1 inpatient (i.e., severe exacerbations) or ≥2 outpatient events (includes ED)

We will describe the formation of the study cohort. Patient characteristics at baseline in patients treated with Stiolto and patients treated with Trelegy will be assessed separately using standard descriptive statistics.

Propensity scores including both pre-specified and data-derived variables will be then calculated. Balance of patient characteristics between the cohorts will be described before and after propensity score application and compared using standardized differences. For each Stiolto patient, a Trelegy patient with the closest available propensity score will be selected. Nearest neighbor matching method with a caliper of 0.2 will be utilized. Standardized differences greater than 0.10 (10%) will be taken to indicate imbalance, and these variables will also be included in outcome models, categorized as appropriate.

For the analysis of the primary objective, a Cox proportional hazard regression model will be used to perform an as-treated analysis that assesses the effect of first line maintenance medication with Stiolto versus the first line maintenance medication with Trelegy on the time to first COPD exacerbation. This estimates the HR of a COPD exacerbation associated with Stiolto use relative to Trelegy use, along with 95% CI. Based on the days' supply post index date, allowing a grace period of 45 days following the end of days' supply to account for intermittent use.

Stratified analyses will be using the same approach as the main analysis. Calculation of propensity scores will be repeated within the subset of the cohort with available results to create weighted populations suitable for these stratified analyses.

The analysis of the secondary objective related to the risk of pneumonia will also be assessed using Cox proportional hazard regression models with an as-treated approach, like that of the primary analysis.

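### Under the Section 9.3 definitions, recorded exacerbation history is cut short for patients first coded with COPD at index, and no listed covariate or stratum rule takes account of the COPD-coded look-back

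*Combined protocol and SAP*

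**What the plan says.** Section 9.2.2 asks for two medical claims with a COPD code, "at least one claim on index date or before in the baseline period". The codes may be for "COPD in any position during the study period (baseline ± post index date"), so the second claim may follow index. A single COPD claim on the index date is enough baseline evidence.

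Section 9.3 defines exacerbations through COPD-coded encounters. The first severe route is "An inpatient admission or an ER visit with a COPD diagnosis code in the primary position". The other two start from a primary diagnosis of acute respiratory failure and need a COPD code on the same encounter, or on another inpatient or ER encounter within 7 days. All three moderate routes need an ambulatory visit with a COPD code plus an oral corticosteroid (OCS), an antibiotic or both, for example "An office or outpatient visit with a COPD diagnosis code in any position + a pharmacy claim for respiratory antibiotic prescription".

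Section 9.3.2.1 gives a different moderate definition for the primary outcome: "An antibiotic for a respiratory condition dispensed", with or without an OCS and with no COPD-coded visit stated. Its severe routes all still need a COPD diagnosis. The episode rules after Appendix 3 refer to Section 9.3.2.1.

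The baseline count is used twice. Section 9.3.3 puts "Previous acute COPD exacerbation (measured both overall and in the 30 days prior to cohort entry") into the propensity score as 0, 1 or ≥2. Section 9.7.1 defines the Low stratum as "0 inpatient (i.e., severe exacerbations) and 0-1 outpatient events (i.e., moderate exacerbations") and the High stratum as at least one inpatient event or at least two outpatient events, with ED visits counted among the latter. Neither section says which exacerbation definition applies.

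**The concern.** A recorded zero can mean two things. In a patient with a year of COPD-coded claims it is evidence of no exacerbation. In a patient first coded at index it may only mean that earlier chest episodes were coded as bronchitis, dyspnea or pneumonia. The plan treats both zeros alike. No covariate listed in Section 9.3.3 records how long the patient had been COPD-coded.

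This matters because Section 7 names prior exacerbations (two or more moderate, or one severe) as the ground for considering triple therapy, and Section 9.9 accepts that confounding by indication could be an issue. The standardized-difference check compares recorded values, so by itself it cannot separate a true zero from an unobservable one. The Low stratum then mixes patients with truly low history and patients whose history could not be seen. That weakens the question in Section 7, which asks for evidence on specific patient subsets.

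**Working it through.** The plan states no figure on this point, so there is none to reproduce. The check applies its definitions to one type of patient and then gives an illustrative range.

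**1. What can be counted.** Take a patient whose first COPD code is on the index date. Section 9.3.1 runs baseline from 364 days before index through index, so index-date encounters belong to it. Qualifying events lie on the index date or within 7 days of it, and the 14-day merging rule makes them one episode. The last column adds two earlier antibiotic courses without a COPD code, each more than 14 days from any other event.

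| Index-date COPD encounter | Section 9.3 | Section 9.3.2.1, two earlier uncoded antibiotic courses |
|---|---|---|
| Office visit, no OCS or antibiotic | 0, Low | 2, High |
| Office visit, antibiotic on that day or in the 7 days before | 1, Low | 3, High |
| ED visit, primary COPD | 1, Low* | 3, High |
| Admission, primary COPD | 1, High | 3, High |

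*An ED visit is severe in Section 9.3, but Section 9.7.1 counts it as an outpatient event, so one visit reads as Low.

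Under Section 9.3 the earlier courses change nothing and ≥2 cannot be reached. High needs an index-date admission or, by the third severe route, a respiratory-failure admission in the preceding 7 days paired with a COPD-coded inpatient or ER encounter at index. Under Section 9.3.2.1 the problem largely disappears for antibiotic-treated episodes. It remains for OCS-only episodes and for earlier admissions or ED visits without a COPD code.

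**2. Possible number mislabelled, under Section 9.3.** The matched sample in Section 9.5 is 2 × 3018 = 6036. Let f be the share first coded on the index date and h the share of those with a truly High history. Both are assumptions, and all such patients are taken as labelled Low.
- Mislabelled = 6036 × f × h
- f = 0.05, h = 0.10: 30 patients
- f = 0.30, h = 0.40: 724 patients

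**3. Possible effect on the overall hazard ratio (HR, Stiolto/Trelegy).** Let pS and pT be the hidden High shares among newly coded Stiolto and Trelegy patients, and R the risk ratio carried by such a history. All are assumed, before any correction by other covariates.
- Spurious HR = (1 + f·pS·(R−1)) / (1 + f·pT·(R−1))
- pS = pT: 1.00, no bias
- f = 0.05, pS = 0.2, pT = 0.3, R = 1.5: 1.005/1.0075 = 0.998
- f = 0.30, pS = 0.2, pT = 0.4, R = 2.0: 1.06/1.12 = 0.946
- With the arms exchanged, the last two become 1.002 and 1.057

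If instead the newly coded share itself differs (30% Stiolto, 20% Trelegy) and these patients have r times the hazard of others, the factor is (1 + 0.3(r−1))/(1 + 0.2(r−1)): 0.91/0.94 = 0.968 for r = 0.7 and 1.09/1.06 = 1.028 for r = 1.3. The direction is therefore not known either.

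**The case against.** A reader might infer that history can be counted only on COPD-coded claims. Section 9.3.2.1 contradicts this for antibiotic-treated moderate events, and the episode rules cite that section. The point survives in narrower form: Section 9.3.2.1 is written for events after cohort entry, Sections 9.1 and 9.2.2 tie moderate events to an office or outpatient visit, and Section 9.3.3 names no definition. Severe events need a COPD code under either text.

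A reader might also infer that newly coded patients are forced to no history and into Low. They are not. Index-date claims belong to baseline, so a count of 1 is possible, and a qualifying admission gives High.

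The strongest defence is that the propensity score holds covariates that need no COPD code: OCS, respiratory antibiotics, short-acting drugs, oxygen, acute bronchitis, pneumonia and dyspnea. A patient with hidden treated episodes should differ on several of these. Section 9.7.1 adds unspecified data-derived variables and recalculates the score within strata, so the comparison inside Low is partly protected too. Sections 9.7 and 9.9 allow prognostic-factor sensitivity analyses and bias analysis. This stands for the matching, so it cannot be said that balance checks would miss the problem entirely. It does not repair the stratum labels, and none of the optional analyses is specified for this group.

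**Conclusion.** The point holds as a gap that is cheap to close, not as a demonstrated error. Under Section 9.3, patients first coded at index have a baseline history truncated to at most one episode and are mostly labelled Low. Under Section 9.3.2.1 the truncation is confined to severe and OCS-only events. The plan does not say which applies.

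The stronger reading, that the overall HR is biased, is not supported. It needs a difference between arms in the newly coded share or in hidden history, and the documents give no figure for either. The range of 30 to 724 mislabelled patients and the HR factors between 0.946 and 1.057 rest wholly on assumed inputs, and partial correction by the other covariates would pull the factors toward 1. The blurring of the Low stratum needs no such difference. It follows from the definitions wherever newly coded patients have uncounted episodes.

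**What to change.** 1. Reconcile Section 9.3 with Section 9.3.2.1, and state in Sections 9.3.3 and 9.7.1 which definition sets the prior-exacerbation covariate and the Low/High strata.
2. Derive the time from first COPD-coded claim to index within the fixed 12-month baseline, either continuous or in bands such as 0–30, 31–180 and more than 180 days. The documents suggest no cut-points, so these are only an example. Add it to the propensity score and the balance table, reported by arm.
3. Repeat the Low/High analysis, as a sensitivity analysis, in patients with a COPD-coded claim more than 180 days before index.

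The cost is one derived variable from claims already extracted and one extra table. The restricted analysis will have fewer patients and describes a narrower population (coded for over 180 days before first maintenance use), so it should be read beside the main result, not in place of it.

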7. RATIONALE AND BACKGROUND

Chronic obstructive pulmonary disease (COPD) is a leading cause of morbidity and mortality throughout the world.¹ COPD has risen to become the third leading cause of death in the United States (US). ^{2,3} The Global Initiative for Chronic Obstructive Lung Disease (GOLD) 2020 report and the American Thoracic Society 2020 report recommends dual bronchodilator therapy (DBT) with long-acting muscarinic antagonists (LAMAs) plus long-acting beta2-agonists (LABAs) for patients with COPD who have persistent symptoms and/or exacerbations on LAMA or LABA monotherapy. ^{4,5} Consideration of escalation to triple therapy (TT; LAMA+LABA+inhaled corticosteroids [ICS]) is recommended in case of further exacerbation (\geq 2 moderate exacerbations or 1 severe exacerbation) and after assessing the risks/benefits. An important consideration is the trade-off between preventing exacerbations to restrict TT use further, to only patients who are likely to respond to ICS (such as \geq 2 moderate exacerbations or 1 severe exacerbation in the previous year, to those with asthma-COPD overlap or elevated blood eosinophils. ⁷

Page 17 of 47

c38026921-01

Proprietary confidential information © 2022 Boehringer Ingelheim International GmbH or one or more of its affiliated companies

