Several trials compared a single-inhaler fixed dose combination (FDC) TT with an open combination of TT (ICS/LABA plus LAMA) respectively and found a small degree of greater benefit with FDC TT.⁸ Several Randomized Controlled Trials (RCTs) assessing the comparison of DBT LAMA-LABA to TT FDC of LAMA-LABA-ICS inhalers reported fewer exacerbations over one year with TT FDC. 9,10,11 However, these findings are complicated by methodologic issues related to the withdrawal of maintenance treatment at randomization, inclusion of patients with history of asthma and around at least 40% -70% utilizing ICS before entering the clinical trials. $\frac{12,13,14}{12}$ TT is associated with 53% greater risk of pneumonia compared to DBT and is frequently used inappropriately, including overuse in certain COPD patients. 15,16,17,18,19 Approximately 13% -15% of maintenance treatment naïve patients are prescribed FDC TT as first line long-acting maintenance medication (Data on File) contradicting guideline recommendations and irrespective of the safety concerns. We believe a major reason of that practice pattern is just out of convenience as FDC TT are now available in the market. and certain pharmaceutical companies are encouraging early prescribing of triple therapy, including amongst primary care physicians. Any deviation in pharmacological management, particularly maintenance treatment initiation of COPD patients that is different from GOLD 2020 or ATS 2020 strategy document for the management of COPD may have both clinical and economic consequences.²⁰

Given the high-cost side effect associated with long-term use of ICS and inconsistent evidence concerning whether there is a clinically relevant benefit of ICS combination therapy in terms of COPD disease control, it is important to assess differences between subsets of COPD patients in terms of the effectiveness and cost of FDC TT versus other non-ICS options, such as FDC DBT (e.g., Tiotropium+Olodaterol).

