9.2.2 Study Population

Patients initiating Stiolto, or Trelegy will be identified using pharmacy claims (database). The date of the first prescription claim (on or after 15th September 2017) will be defined as the index date. Patients will be required to have a diagnosis of COPD (ICD-9-CM: 491.xx, 492.xx, 496.xx; ICD-10-CM: J41-J44) on two separate medical claims. Patients 40 years or older will be included in the study. Patients will be required to have continuous enrolment for 12 months prior to the index date. Patients will be excluded if they show any use of COPD maintenance medications (ICS, LABA or LAMA in any combination), during the baseline period of six months pre-index date. This will satisfy the criteria for being considered as treatment naive. Patients with two separate medical claims with a diagnosis of asthma, lung cancer, interstitial lung disease, or cystic fibrosis during the study period will be excluded. Using propensity score matching (PSM) technique, we will develop matched cohorts of patients between Stiolto initiators and Trelegy initiators. We will conduct 1:1 matching using nearest neighbour matching approach with a caliper of 0.2. Exacerbation will be defined as a COPD hospitalization (severe exacerbation) or Emergency Department (ED) visit (severe exacerbation) with COPD, or use of approved respiratory antibiotics (e.g., Azithromycin) \pm Oral CorticoSteroids (OCS) medications within ± 7 days of the

Proprietary confidential information © 2022 Boehringer Ingelheim International GmbH or one or more of its affiliated companies

office/outpatient visit (moderate exacerbation) as the primary diagnosis. Multiple exacerbations occurring within 14 days of each other will be considered as a single exacerbation and will be per the higher severity.

Patients will be followed after the index date to record time to first incidence of exacerbations, record time to first incident case of pneumonia, and HCRU. The analysis will be, "on treatment", analysis. Patients will be followed from the index date until the earliest of the first occurrence of outcome event, switch in index treatment (Stiolto or Trelegy), discontinuation of index treatment (Stiolto or Trelegy), the end of the study period, the end of continuous health plan eligibility, or (for main analyses) one year after index date. Hazard ratios and their 95% CI from proportional hazards models will be used to assess differences in the risk of COPD exacerbation and pneumonia.

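### Adjustment for the single-claim asthma patients whom the exclusion rule keeps is neither pre-specified nor guaranteed, because asthma is not a named propensity covariate

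*Combined protocol and SAP*

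**What the plan says.** **Eligibility.** Section 9.2.2 (Exclusion Criteria) will "exclude all patients with two medical claims of asthma, cystic fibrosis, lung cancer, or interstitial lung disease". The two claims may carry the code anywhere on the claim, must fall on different dates, and are counted across the study period. The narrative in sections 9.1 and 9.2.2 gives the same two-claim rule. The COPD inclusion criterion in section 9.2.2 glosses the study period as baseline with or without post-index time.

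**Why asthma matters to this plan.** Section 7 reports recommendations to confine triple therapy to patients likely to respond to an inhaled corticosteroid, and extends this "to those with asthma-COPD overlap or elevated blood eosinophils". It also lists "inclusion of patients with history of asthma" among the methodologic problems of the randomized trials.

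**Adjustment.** Section 9.3.3 says: "The covariates included in the Propensity Score Matching (PSM) will include all the below covariates". The list covers demographics, prior exacerbations, respiratory drugs, antibiotics, oral steroids, oxygen, rehabilitation and comorbidities including GERD, arthritis, osteoporosis, acute bronchitis and dyspnea. Asthma is not among them. The nearest general item is "Quan-Charlson Comorbidity Index score/individual comorbidities", whose components are not listed.

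**Other provisions.** Section 9.7.1 states: "Propensity scores including both pre-specified and data-derived variables will be then calculated". It gives no candidate list or selection rule for the data-derived part. A characteristic with a standardized difference above 0.10 after matching goes into the outcome model (sections 9.2.4, 9.7 and 9.7.1).

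**The concern.** By the plan's own account, asthma is linked both to the choice of triple therapy and to response to an inhaled corticosteroid. It can also be measured here, since the exclusion rule already reads the asthma codes. It is unlike the confounders that section 9.9 lists as unavailable (body mass index, smoking, symptom scores, lung function).

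If single-claim asthma patients lean toward Trelegy and also differ in exacerbation risk, part of that difference would appear in the primary hazard ratio as a drug effect. The balance check would not reveal it, because it works on the characteristics that are tabulated. The stake is a modest, avoidable confounding path in the primary comparison, in a study that criticizes earlier trials for a related weakness.

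**Working it through.** The plan gives no figure on this point to reproduce, so the check is a reading of the rules followed by a bias calculation on assumed inputs.

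**Who is kept.** Two asthma claims on separate dates within the study period exclude a patient. One baseline claim plus one post-index claim on another date therefore also excludes. Those kept with an asthma signal in baseline are the patients for whom that is the only asthma claim in the study period.

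**What could adjust for them.**
- The named list (9.3.3): no asthma item.
- Data-derived variables (9.7.1): possible, but unspecified. Section 9.2.4 describes matching on a pre-specified list only.
- Listed respiratory drugs as proxies: partial. Any ICS or LABA use in the six months before index excludes the patient, so the ICS and ICS/LABA covariates can vary only through use earlier in the 12-month baseline. Short-acting drugs and oral steroids are not limited in this way.
- The 0.10 check: acts only if asthma is among the characteristics examined.

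**Size.** Let pS and pT be the shares with one asthma claim in the matched Stiolto and Trelegy groups, and HR the asthma-exacerbation hazard ratio. All three are assumptions. The approximate bias factor on the Trelegy/Stiolto ratio is

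B = [1 + pT(HR − 1)] / [1 + pS(HR − 1)],

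and the standardized difference is

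d = (pT − pS) / √{[pT(1 − pT) + pS(1 − pS)]/2}.

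| pS / pT | HR | B | d |
|---|---|---|---|
| 1% / 2% | 1.2 | 1.004/1.002 = 1.002 | 0.08 |
| 3% / 5% | 1.2 | 1.010/1.006 = 1.004 | 0.10 |
| 3% / 6% | 1.2 | 1.012/1.006 = 1.006 | 0.145 |
| 5% / 10% | 1.3 | 1.030/1.015 = 1.015 | 0.191 |
| 6% / 15% | 1.5 | 1.075/1.030 = 1.044 | 0.297 |
| 5% / 15% | 3.0 | 1.300/1.100 = 1.182 | 0.338 |

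The last row is an extreme, shown only to bound the range. The plan estimates Stiolto relative to Trelegy, so the factor on its hazard ratio is 1/B. Rows three to five give 1/1.006 = 0.994 to 1/1.044 = 0.958, in favour of Stiolto. For scale, the cited cohort study of triple versus dual therapy (section 9.5) reports 0.97 (95% CI 0.87 to 1.08). Multiplying 0.97 by 1.006 to 1.044 gives about 0.976 to 1.013, well within that interval.

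**Loss of pairs in a sensitivity analysis.** Section 9.5 expects 3018 matched pairs. If asthma status were independent within pairs and broken pairs were simply dropped, the loss would be:
- at 3%/6%: 1 − 0.97 × 0.94 = 8.8%, about 266 pairs, leaving 2752;
- at 6%/15%: 1 − 0.94 × 0.85 = 20.1%, about 607 pairs, leaving 2411.

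Both stay above the 2000 per cohort that section 9.7 requires before the comparative analysis.

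**The case against.** The strongest reply is that asthma is already controlled by restriction. Repeated asthma coding anywhere in the study period removes the patient, and the plan likewise asks for two claims to accept a COPD diagnosis. A lone code may be a rule-out or a coding error, and it is not the asthma-COPD overlap that section 7 names. The propensity list holds several correlates of asthma, data-derived variables may add it, section 9.7 allows sensitivity analyses on prognostic covariates, and section 9.9 admits residual confounding and promises bias analysis.

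Much of this stands. A reader might infer that asthma stays wholly unadjusted, or that the study repeats the flaw it finds in the trials. The documents support neither: the two-claim rule removes the clearer cases, and part of the remainder may be captured. A reader might also infer that the balance limit would be breached. That follows only from assumed splits remaining after matching; 1% vs 2% would pass.

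A further tempting argument is that better steroid response in these patients pulls the overall hazard ratio down. Taking the 0.66 that section 9.5 reports for high eosinophils as a stand-in for 3% to 8% of patients, exp[(1 − q) ln 0.97 + q ln 0.66] gives about 0.96 to 0.94. But this is effect modification in a mixed population. Propensity adjustment would not remove it, and the documents give no asthma-specific hazard ratio.

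What the reply does not explain is why a variable that the plan treats as relevant, and already has in hand, is missing from both the matching list and the balance table. The safeguards it relies on are optional or unspecified, and none names asthma.

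**Conclusion.** The point holds in a limited form. Patients whose only study-period asthma claim falls in baseline are kept, and adjustment for that signal is neither pre-specified nor guaranteed. The size is unknown, because the documents report neither how many such patients there are nor how they divide between arms. Under the assumed splits of 3% vs 6% to 6% vs 15% and asthma hazard ratios of 1.2 to 1.5, confounding is about 0.6% to 4.4%; with smaller splits it is negligible. These figures treat asthma as independent of the matched covariates, so partial capture by proxies would reduce them.

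Net direction is also open. Higher baseline risk among Trelegy users would favour Stiolto, while better steroid response would act the other way, by a route that matching does not address. This is a worthwhile improvement to the covariate list, not a demonstrated bias in the primary result.

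**What to change.** Keep the two-claim exclusion. Add one indicator, any asthma claim in the baseline period (index − 364 through index), to the section 9.3.3 propensity list and to the balance table, so that the 0.10 rule applies to it. As a sensitivity analysis, exclude every patient with a baseline asthma claim, rematch, and repeat the primary Cox model.

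The indicator uses claims already processed, but it needs its own baseline window because the exclusion runs over the whole study period. The rerun loses some matched pairs, in the sensitivity analysis only. Tabulating the indicator by arm before and after matching would also supply the prevalence and split that the plan now lacks, and so show whether the issue matters.
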